13. Alcohol consumption > 2 alcohol units⁵ for males and > 1 alcohol unit for females per day.
14. Mental illness or drug abuse in anamnesis.
15. Bariatric surgery in anamnesis, any surgery for 3 months before enrollment.
16. Pregnancy, breast-feeding; childbirth less than 3 months before enrollment.
17. Participation in other clinical trials for 3 months before enrollment in this study.
18. Patients who are related to any of the on-site research personnel directly involved in the conduct of the trial or are an immediate relative of the study investigator. ‘Immediate relative’ means husband, wife, parent, son, daughter, brother, or sister (regardless of whether they are natural or adopted).

⁵ 1 alcohol unit – 15 g of ethanol or approximately 40 g of hard liquors or 140 g of wine or 300 g of beer.

19. Patients who work for MATERIA MEDICA HOLDING (i.e. the company's employees, temporary contract workers, appointed officials responsible for carrying out the research or immediate relatives of the aforementioned).

Criteria for Withdrawal or Termination

1. Screening failure.
2. Acute or exacerbation/decompensation of chronic disease of any etiology, with clinically relevant symptoms persisting for more than 5 days.
3. Inability or refusal of patient to comply with the protocol requirements.
4. Necessity in medical products prohibited within the study.
5. Development of adverse event requiring cancellation of investigational product.
6. Desire of patient to complete the study ahead of schedule due to inefficacy of therapy or any other reason.
7. Pregnancy.
8. Cases not specified by the protocol when, according to the investigator's opinion, further participation in the study harms the patient.
9. Incorrect inclusion of ineligible patient.
10. Participation in another clinical study.
11. Unblinding.

Number of subjects

It is planned to include 842 patients, which is expected to allow at least 286 patients (143 patients in both groups - Subetta and Placebo) to complete all protocol procedures.

Interim analysis

The study provides 1 intermediate "non-blind" analysis. At the request of the sponsor, a blind interim analysis can be performed to clarify population characteristics and possible correction of the sample size (only in the direction of increase).

Treatment

Group 1

Name of the medicinal product: Subetta

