Safety population: all patients who received at least one dose of the study drug. This sample will be used for the study treatment **safety and tolerability analyze**, since all the AEs identified after the study drug administration will be recorded.

Full Analysis Set. This sample includes all enrolled and randomized patients, except for those who met at least one of the following criteria:

- 1) non-compliance with inclusion / exclusion criteria;
- 2) the patient has not taken as minimum a single dose of the study drug;
- 3) lack of any data of the patient after prescription of the study drug.

This sample is the most consistent with the “Intention-to-treat” principle, will be used for the **Intention-to-treat analysis (ITT analysis) of the the study therapy efficacy**.

Per protocol set. This sample includes all patients who completed the therapy as per the study protocol without any missing scheduled visits. This sample will be used for the **Per Protocol analysis (PP- analysis) of the the study therapy efficacy**.

Per Protocol set will not include the patients whose data are completely or partially invalid for analysis due to a protocol deviation.

Protocol deviations that lead to complete or partial data invalidity:

1. Violation of visit schedule.
2. Inappropriate distribution/supply of the study drug.

⁶ Licensee: OOO "NPF "Materia Medica Holding", No. 70100045

3. Administration of prohibited therapy.
4. Increase or decrease $\geq 25\%$ in the amount of the study therapy administered.
5. Inability to assess the patient's compliance using the formula (e.g. loss of pack with the product).
6. Major discrepancies between source documents and CRF detected during monitoring or another authorized check.
7. Violation of the procedure for obtaining Informed consent.
8. Non-compliance with the clinical study protocol procedures.
9. Inability to collect all patient's data used for evaluation of the study endpoints (e.g. lack of entries in source documents required for verification of inclusion/exclusion criteria, safety and efficacy criteria).
10. Other protocol deviations resulting in full or partial data invalidity.

Evaluation of sample size

The sample size has been assessed on the basis of the following rules and assumptions:

1. Statistical provisions.
 - 1.1 the power of the statistical tests " $P = (1 - \beta)$ " is assumed to be 80% (the probability of correct rejection of the null hypothesis is 0.8);

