 - 1.2 the probability of a type I error " α " is allowed to be less than 5% (the probability of the erroneous acceptance of an alternative hypothesis is less than 0.05);
 - 1.3 the statistical tests are 2-sided unless otherwise specified;
 - 1.4 the calculation of the sample size is based on the assumptions about the expected effects, declared in the primary efficacy endpoint of the Protocol;
 - 1.5 the ratio between the sample sizes of Subetta and Placebo groups is 1:1 (1 Subetta patient - 1 Placebo patient);
 - 1.6 statistical hypotheses - null and alternative hypotheses on superiority of the study product over placebo under the dosing regimen used
 - 1.7 one unblinded interim analysis on 50% sample was expected allowing to terminate the study both due to the effect confirmation (according to O'Brien-Fleming) and due to acceptance of null hypothesis (Pocock).

a) primary endpoint:

$$H_0: \Delta\mu_1 - \Delta\mu_2 = 0$$

$$H_a: \Delta\mu_1 - \Delta\mu_2 \neq 0$$

where $\Delta\mu_1$ - mean reduction (initial – final score) in Subetta group,

$\Delta\mu_2$ – mean reduction (initial – final score) in Placebo group;

1.8 calculation of sample size for statistical criteria will be made using the following formula:

$$n_1 = kn_2$$
$$n_2 = R \frac{(z_{\alpha/2} + z_{\beta})^2 * (1 + 1/k) * \sigma^2}{\epsilon^2}$$

where n_1, n_2 is sample size in IP and placebo groups, respectively

$\epsilon = \Delta\mu_1 - \Delta\mu_2$ is expected difference between mean reductions of value between Subetta and Placebo groups

k – coefficient of Subetta/Placebo sample ratio (1 : 1)

σ – standard deviation of reduction

$z_{\alpha/2}$ – tabular value of two-sided z-test for α

z_{β} – tabular value of one-sided z-test for β , R-coefficient taking into account interim analysis depending on the accepted functions of error and analysis position (in this design equal to 1.1334).

1.9 terminal sample size was determined using the formula:

$$N_T = N_{PP} / (1 - R_w)$$

where N_T – terminal sample size

N_{PP} – result of calculation in cl. 1.8, i.e. scheduled number of subjects completing the study per protocol

R_w – withdrawal rate.

2. Assumptions on expected clinical study effects: difference in reduction of 2-hour plasma glucose (at OGTT) between Product and Placebo groups will be no less than $\epsilon = 1.1$ at standard deviation of $\sigma = 3.11$.

A priori estimates for tested parameter variables in the groups:

Primary endpoint:

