Changes in 2-hour fasting plasma glucose (OGTT) at 12 weeks vs. baseline.

Placebo group:

characteristics of 2-hour plasma glucose level (at OGTT) at the start of the study.

SD=0.94 [39]

After 3 months

SD=2.3 [1.87; 2.987] [40]

Change (3 m) -0.2 [-1; 0,6] [40]

Standard deviation of change in 3 months (in assumption of independence of scoring for DM)

SD_Δ~311.

Study drug group:

Based on interim study, change in glucose level in experimental group in 3 months was:

Change (3 m) = 1.96 [1,7; 2,22]

Let us take standard deviation of change in experimental group similar to control group.

Software code for evaluation of sample size:

Proc seqdesign errspend;

Design nstages=2

Info=cum(0.5,1)

Method(alpha)=UNI(rho=0.5 tau=0)

Method(beta)=UNI(rho=0 tau=0)

Stop=both

Alpha=0.05

Beta=0.2;

Samplesize model=twosamplemeans(meandiff=1.1 stddev=3.11);

Run;

Therefore, the value of expected effect is rated as $\epsilon_{\Delta}=1.1$ mmol/L (the most conservative scoring) – the worst case for Subetta and the best for Placebo) at standard deviation $\sigma_{\Delta}=3.11$ mmol/L. Thus, sample size will be 143 subjects per study group. Taking into account the claimed withdrawal coefficient, this will require enrollment of 842 subjects.

Therefore, overall size of the required sample will be 842 subjects ensuring the study completion per protocol by at least 286 subjects.

Therefore, the sample size has been found to be (143) patients in each of the groups (Product and Placebo) to estimate superiority of the study drug over placebo.

Taking into account potential withdrawal of at least 66% subjects⁷ (Cw=0.66) during the study for various reasons, at least 842 patients should sign PIS and ICF.

Statistical criteria

All statistical calculations will be performed using two groups of statistical criteria:

- parametric – to obtain effective estimates for random parameters in case the relevant conditions of method/model applicability are not violated (e.g. sphericity, normality, risk proportionality, etc.);

⁷ Based on blinded interim analysis.

- non-parametric – in all other cases.

Parametric criteria

The application of parametric criteria will be accompanied by a check of models for applicability (e.g. Kolmogorov-Smirnov test, Shapiro-Wilk test).

The following parametric methods and approaches are to be used:

1. To assess the differences of continuous variables obtained in one group at two different visits – Student t-test for paired samples.

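### Does inflating 286 completers to 842 consents with a single 66% loss leave the trial short of its 80% power?

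*Combined protocol and SAP*

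**What the plan says.** Evaluation of sample size, clause 1.9, divides the number finishing per protocol by one minus a withdrawal rate. The text after the SAS code sets that rate at 0.66: "Taking into account potential withdrawal of at least 66% subjects", with footnote 7 giving a blinded interim analysis as its source. The same sentence concludes that "at least 842 patients should sign PIS and ICF".

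The 842 is described differently elsewhere. Number of subjects says "It is planned to include 842 patients, which is expected to allow at least 286 patients", and an earlier line of the sample-size section says "this will require enrollment of 842 subjects". The first item under Criteria for Withdrawal or Termination is "Screening failure", so a patient who signs consent and fails screening counts as a withdrawal.

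Clause 1.7 places the unblinded interim analysis at half the sample, and the code sets the information fractions to 0.5 and 1. The document states no screening-failure rate, no post-randomisation dropout rate and no number to randomise.

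**The concern.** Two things look wrong at first.

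- **The wording of the loss.** A lower bound on loss gives an upper bound on completers. If 66% or more are lost, 842 patients yield about 286 or fewer, yet the plan says that 842 secures 286 or more. The two statements agree only if the loss is no higher than 66%.
- **The pooled rate.** The 842 is counted at consent and the 286 at per-protocol completion, so one rate has to absorb screening failure, dropout and protocol deviations. Without a split, the reader cannot say how many patients will be randomised. Because 842 is also called included or enrolled, one might fear that two thirds of the randomised patients are lost. The interim at half the sample might likewise be read as 421 consents instead of 143 completers.

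At stake would be the stated 80% power and, on the worst reading, the integrity of the randomised comparison.

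**Working it through.** **Inputs, all from Evaluation of sample size.** Difference 1.1 mmol/L and SD of change 3.11 ("Samplesize model=twosamplemeans(meandiff=1.1 stddev=3.11"); two-sided alpha 0.05; power 80%; 1:1 allocation; R = 1.1334 for the interim look; loss 0.66.

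**The plan's own figures.**

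- Fixed design, per group: 2 × (3.11 × (1.960 + 0.842) / 1.1)² = 125.5.
- With the interim factor: 125.5 × 1.1334 = 142.2, rounded up to 143 per group, 286 in total.
- R checked by numerical integration of the two-stage design (O'Brien-Fleming-type efficacy boundary, Pocock-type binding acceptance boundary, look at 50%): 1.1334.
- Inflation: 286 / (1 − 0.66) = 841.2, rounded up to 842.

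Every stated figure reproduces.

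**Slack.** 842 × 0.34 = 286.3, so there is almost none. The break-even loss is 1 − 286/842 = 66.03%.

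**Sensitivity to the loss**, with 842 signers and the same two-stage boundaries. The last column is the binomial chance of 286 or more completers.

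| Total loss | Completers | Power, SD 3.11 | Chance of 286 or more |
|---|---|---|---|
| 66% | 286 | 80.2% | 52% |
| 67% | 278 | 79.1% | 29% |
| 68% | 269 | 78.0% | 12% |
| 70% | 253 | 75.4% | under 1% |
| 75% | 211 | 68.0% | under 1% |

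Between 66% and 70%, power falls by a little over one percentage point for each extra point of loss.

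**How conservative the SD is.** Under the plan's assumption of independent measurements, the upper limit of the follow-up SD gives √(0.94² + 2.987²) = 3.13, close to the 3.11 used. The central value gives √(0.94² + 2.3²) = 2.48. At 2.48, power is 92.0% at 68% loss, 90.5% at 70% and 85.2% at 75%.

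**Which patients the 842 counts.** The sentence that derives the requirement ties it to signed consent. Under Samples, the Total set is made up of included patients who signed consent, so included fits the same meaning. The Full Analysis Set definition names enrolment and randomisation separately, so enrolled need not mean randomised. Screening failure is a listed withdrawal. Together these make consent the natural reading.

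**Number to randomise.** For assumed post-randomisation losses of 5%, 10%, 20% and 30% (the document gives none), 286 / (1 − loss) is 302, 318, 358 and 409. All leave 286 completers as the target.

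**Interim.** Half of 842 is 421 consents, and 421 × 0.34 = 143.1. At the planned loss, both readings give about 143 completers once those patients have finished follow-up. Clause 1.7 also comes before the inflation in clause 1.9 and matches the 0.5 information fraction in the code, so half of the 286 is the evident meaning.

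**The case for a change.** The strongest case for a change is that the plan promises something its own words do not support. Even at a true loss of exactly 66%, reaching 286 completers is close to an even chance, so the claim that 842 secures them is too strong. The only stated recruitment figure counts people who may never be randomised. The blinded increase is optional, at the sponsor's request, and is not tied to a completer count. A stated number to randomise would be cheap to add and easier to monitor.

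Much of this is accurate as description. The minimum wording on the loss is a slip, the composition of the 66% is not reported, and no number to randomise is given.

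It does not amount to a defect in the design. Any trial loses power if attrition exceeds its planning rate, and this rate was taken from the trial's own blinded data. Nothing says recruitment closes at 842: the figure is worded as a minimum, and a loss of at least 66% does require at least 842 signatures, so that sentence is coherent in itself.

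The fear that about 556 randomised patients (842 × 0.66) would lack a week-12 glucose value needs 842 to mean randomised patients. It also treats per-protocol loss as missing data, although many exclusions from the Per protocol set (visit timing, a lost pack, record discrepancies) can leave that value in hand.

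The possible remedies gain little. Rewording the loss as at most 66% would assert a bound that nobody has shown. A split of the rate needs interim data that the document does not contain. Fixing the interim at half the completers restates the code.

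**Conclusion.** No change is needed. At the assumed 66% loss, 842 consents give the stated 286 completers and 80.2% power, and 143, 1.1334 and 842 all reproduce. A shortfall needs a loss above the planning value. It would be modest up to 70% (75.4% power at the conservative SD), and the plan has an open-ended consent count and an optional blinded increase with which to respond.

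What remains is clerical. The 66% is best read as the expected total loss from consent to per-protocol completion, and 842 as the expected number of consents. A final report would normally give the screening-failure and post-randomisation components and the number randomised.

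This rests on two assumptions: that 842 counts consents, which the document supports in several places without defining it outright, and that the blinded look's 66% is a fair forecast, which cannot be checked from the document. If 842 were shown to mean randomised patients, the conclusion would have to be revisited.

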2. To assess the temporal dynamics of the compared values – analysis of variance (ANOVA) or covariance (ANCOVA) in the modification with repeated measures.
3. In case of multiple comparisons between the groups will apply a variety of corrections for multiplicity Dunnett, Tukey, Scheffe, Holm adaptive test, etc.
4. In case of abnormal data distribution, approaches with the Generalized Linear Models and /or Mixed Linear Models will be used.
5. Selection of the type of distribution, clarification of the factor and covariance structures of the model is carried out with fit statistics such as AIC (Akaike information criterion).

To perform the above-mentioned statistical tests and techniques, it is assumed that the following SAS procedures are used:

- UNIVARIATE – check for normality of the compared distributions;
- CORR, MEANS – calculation of descriptive statistics;
- TTEST – Student t-test with all the modifications;
- GLM – analysis of Generalized Linear Models for studying temporal dynamics (ANOVA, ANCOVA);
- GENMOD – analysis of Generalized Linear Models.
- MIXED – analysis of Generalized Linear Models.

Non-parametric criteria

Below, there are the main types of possible comparisons with the respective criteria:

1. To assess the dynamics of the compared indicators – Friedman test, non-parametric analogue of analysis of variance with repeated measures.
2. For the frequency analysis of 2×2 cross tables – χ^2 -test (if the compared frequencies are greater than 5) or Fisher exact test (if one of the compared frequencies is less than 5).
3. For the frequency analysis of cross tables with independent strata – Cochran–Mantel–Haenszel test (modification of the χ^2 -test for multiple comparisons).

4. For the frequency analysis of data on the presence / absence of an event or outcome during repeated measures (cross tables with dependent strata) – survival analysis.

To perform the above-mentioned non-parametric statistical analysis options, it is assumed that the following SAS procedures are used:

- FREQ – Friedman test, χ^2 -test and / or Fisher exact test; Cochran–Mantel–Haenszel test
- LIFETEST, PHREG – survival analysis
- NPAR1WAY – Mann-Whitney U-test.

Safety parameters

Adverse events recorded during the study will be grouped into frequency tables by severity, seriousness and relationship with the study drug.

Data presentation

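### No between-arm test is assigned to the primary hypothesis, and the plan gives two different routes for non-normal data

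*Combined protocol and SAP*

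**What the plan says.** Evaluation of sample size states the primary hypothesis as a two-sided contrast of mean reductions; the second term is the "mean reduction (initial – final score) in Placebo group". The SAS code there sizes the trial with a two-sample-means model. Item 1.7 adds one unblinded interim analysis at half the sample, able to stop the trial for efficacy or for acceptance of the null.

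Statistical criteria then gives a general menu of methods:

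- Parametric methods apply "in case the relevant conditions of method/model applicability are not violated". Their use comes with a "check of models for applicability (e.g. Kolmogorov-Smirnov test, Shapiro-Wilk test"). No threshold is given, and the two tests are only examples.
- The opening rule for everything else is "non-parametric – in all other cases".
- Parametric item 1 is a paired t-test within one group.
- Parametric item 2 reads "To assess the temporal dynamics of the compared values – analysis of variance (ANOVA) or covariance (ANCOVA) in the modification with repeated measures".
- Parametric item 4 reads "In case of abnormal data distribution, approaches with the Generalized Linear Models and /or Mixed Linear Models will be used".
- Parametric item 5 reads "Selection of the type of distribution, clarification of the factor and covariance structures of the model is carried out with fit statistics", with AIC as the example.
- Non-parametric item 1, for dynamics, is the "Friedman test, non-parametric analogue of analysis of variance with repeated measures".
- The t-test procedure in all its variants, and Mann-Whitney beside NPAR1WAY, appear only in the lists of SAS procedures, with no comparison attached.

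**The concern.** The target is stated but the test is not. An analyst could reach the primary hypothesis through a t-test on change, repeated-measures ANOVA, ANCOVA with unspecified covariates, a generalized or mixed model chosen by AIC, or Mann-Whitney, and could cite this plan for each. The assumption checks and AIC both use trial data, and the plan does not say that this selection is done blinded.

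For non-normal data the plan gives two instructions that do not agree. If the non-parametric one is followed, the only numbered method for a continuous change is the Friedman test. That test works within subjects and does not compare arms.

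This is a Phase III superiority trial with an unblinded look that can end it. Nothing requires the same test at both looks. Two analysts following the plan could reach different stopping decisions or final conclusions from the same data, and a switch to ranks would also move away from the stated target of a difference in means.

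**Working it through.** **1. The plan's own sample size.** Inputs from Evaluation of sample size: two-sided alpha 0.05, power 0.80, difference 1.1, SD of change 3.11, 1:1 allocation, R = 1.1334, withdrawal 0.66.

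- n = 2(1.960 + 0.842)² × 3.11² / 1.1² = 125.48 per group.
- 125.48 × 1.1334 = 142.22, rounded up to 143.
- 286 / (1 − 0.66) = 841.2, rounded up to 842.

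Both stated figures reproduce. The point does not rest on an arithmetic error, and the sizing implies a comparison of two means.

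**2. The interim bound.** Item 1.7 names O'Brien-Fleming for efficacy and Pocock for acceptance of the null, with looks at information 0.5 and 1. Write the efficacy bounds as c√2 and c, the interim futility bound as θ/√2 − (θ − c), and θ for the drift at full information. Requiring 0.025 in each tail under the null and power 0.80, with binding futility, gives c = 1.883 and θ = 2.983. Then R = 2.983² / (1.960 + 0.842)² = 1.1334, the plan's figure. The efficacy bounds are therefore about 2.66 and 1.88.

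**3. How far the candidate tests differ.** Simulation with 20,000 trials per setting and normal data.

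- From the plan: baseline SD 0.94; Week 12 SD 2.3, or 2.987 (the upper limit it quotes); difference 1.1 or 0; 143 per arm at the end, so 72 at the interim.
- Assumed, because the documents do not give it: baseline to Week 12 correlation of 0, 0.3 or 0.6. The plan uses independence only to derive an SD for sizing.

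Disagreement means that at least one of t-test on change, ANCOVA and Mann-Whitney on change is significant and at least one is not. The interim uses the 2.66 bound; the final column is a single look at p<0.05.

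| Week 12 SD | Correlation | Interim stop: t / Mann-Whitney / ANCOVA (%) | Interim disagreement (%) | Final disagreement (%) | Error, best of three (%) |
|---|---|---|---|---|---|
| 2.3 | 0 | 48.6 / 45.6 / 56.8 | 19.2 | 3.8 | 7.3 |
| 2.3 | 0.3 | 61.7 / 58.5 / 61.9 | 9.3 | 1.0 | 6.5 |
| 2.3 | 0.6 | 78.6 / 75.6 / 80.8 | 9.9 | 0.2 | 6.9 |
| 2.987 | 0 | 28.8 / 26.6 / 31.4 | 13.1 | 9.1 | 6.9 |
| 2.987 | 0.3 | 35.1 / 33.0 / 34.9 | 7.6 | 3.9 | 6.0 |
| 2.987 | 0.6 | 45.9 / 43.1 / 51.5 | 16.7 | 4.2 | 7.3 |

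Each test alone has error of 4.7-5.2%. Separate runs differ by up to about a point, so the interim range is best read as roughly 7-19%.

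**4. Skewed data.** In a further simulation with assumed right-skewed Week 12 values (SD 2.965, which gives an SD of change of 3.11 at zero correlation), a shift of 1.1 and correlation 0.3, power was 90% for the t-test and 99% for Mann-Whitney. Best-of-three error was 7.5-8.1% over correlations 0 to 0.6. The generalized or mixed models and AIC selection were not simulated.

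**5. Variance gain from baseline adjustment.** With Week 12 SD s, baseline SD b and correlation ρ, the ratio of ANCOVA to change-score variance is s²(1 − ρ²) / (s² + b² − 2ρsb).

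- ρ = 0: 5.290/6.174 = 0.857 (s = 2.3); 8.922/9.806 = 0.910 (s = 2.987).
- ρ = 0.6: 3.386/3.579 = 0.946; 5.710/6.436 = 0.887.
- The ratio is 1 at ρ = b/s, that is 0.41 or 0.31.

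The gain is therefore 0-14%.

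**The case against.** The plan is more constrained than its menu suggests. It fixes the target, sidedness and alpha, and it sizes on two means. With OGTT only at screening and Week 12, the group-by-visit term of a repeated-measures ANOVA equals a t-test on change. The t-test procedure is listed in all its variants, and in a two-arm trial Mann-Whitney reads naturally as the between-arm comparison. These inferences narrow the gap but do not close it: ANCOVA stands as an equal option in the same item, and the methods are conditional on the data.

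Item 4 could also be read as a parametric fallback tried before ranks. The plan gives no such order.

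A reader might infer that a normality check itself inflates error. The figures do not support that. A fixed Shapiro-Wilk rule (5% per arm, assumed; correlation 0) kept error at 5.0-5.4% in simulation. The weakness here is that the rule is not fixed.

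A reader might also infer that the trial will run at 6-7% error. That requires running all three tests and keeping the best, which nothing in the plan prescribes.

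Finally, the document calls itself a protocol summary. A fuller text may exist, so the gap is shown only for the document supplied, which refers to no other analysis plan.

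**Conclusion.** The concern holds. The primary target is fixed, but no between-arm test is assigned to it, the two instructions for non-normal data conflict, and selection is left partly to trial data in a design with an unblinded stopping look.

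The size is moderate. The three plausible tests disagree on stopping for efficacy at the interim in roughly 7-19% of trials, and on final significance in about 0.2-9%. These figures rest on normal data, a difference of 1.1 mmol/L, the plan's SDs, binding futility and an assumed correlation of 0 to 0.6. The upper interim figure belongs to zero correlation; at 0.3 it is about 7-10%.

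The documents do not show that a test was or will be picked for its result, that error control is already lost, or that ANCOVA will bring a particular gain in precision. This should be fixed, and it is a free improvement rather than a defect that invalidates the design.

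**What to change.** For the primary endpoint, drop the normality gate and the AIC selection, and name one between-arm analysis for both the interim and the final look: ANCOVA of Week 12 change in 2-hour glucose, with treatment as a factor and baseline 2-hour glucose as the only covariate. Report the adjusted mean difference with a confidence interval consistent with the group-sequential boundary.

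Naming any single between-arm test would close the gap, including the unadjusted comparison behind the sample size. ANCOVA is preferred because the plan already lists it, it keeps the difference in mean reductions as the target, and it uses a baseline value already collected.

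Reconcile the opening rule of Statistical criteria with Parametric item 4. Keep Mann-Whitney on change as a sensitivity analysis, and limit the paired t-test and Friedman to within-arm description.

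The cost is SAP wording only. The sample size stays at 143 per group and 842 enrolled, with no added procedures.
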